3.0 Patient Eligibility

3.1 Inclusion Criteria

- 3.11 Age \geq 18 years.
- 3.12 Diagnosis of gynecological cancer of any type or strong suspicion for cancer.
- 3.13 Patients must have begun postoperative oral intake of food prior to registration.
- 3.14 Open laparotomy or laparoscopic surgery undertaken with cancer therapeutic intent (not a subsequent surgery to manage a postoperative complication) that had occurred \leq 7 days prior to registration and that entailed more than a simple hysterectomy.
- 3.15 The following laboratory values obtained \leq 21 days prior to registration.
 - Creatinine \leq 1.5 x the upper limit of normal (ULN)
 - Absolute neutrophil count \geq 1500/mm³
 - Platelet count \geq 100,000/mm³
- 3.16 Ability to complete questionnaire(s) by themselves or with assistance.
- 3.17 Provide informed written consent.
- 3.18 Negative (serum) pregnancy test done \leq 7 days prior to randomization, for women of childbearing potential only.
- 3.19 Willing to provide mandatory baseline blood samples for correlative research purposes (see Section 6.12 and 14.0).

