5.0 Stratification Factors

- 5.1 Patient age: ≥ 65 years vs. < 65 years
- 5.2 Splenectomy and/or rectosigmoid resection: yes vs. no
- 5.3 Optimally debulked cancer (complete nodal and omental removal, as appropriate, with <1 cm of residual tumor, if appropriate): yes vs. no
- 5.4 Cancer type: ovarian vs. endometrial vs. other
- 5.5 Open laparotomy vs. laparoscopic surgery

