6.2 Randomization Procedures

6.21 The factors defined in Section 5.0 will be used as stratification factors.

6.22 After the patient has been registered into the study, the values of the stratification factors will be recorded, and the patient will be assigned to one of the following intervention groups using the Pocock and Simon dynamic allocation procedure which balances the marginal distributions of the stratification factors between the intervention groups [16].

- Oral Serum Bovine Immunoglobulin (SBI)
- Placebo

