7.0 Protocol Intervention

7.1 Dosing Intervention Schedule**

Agent	Dose	Route	Day	Retreat
Serum bovine immunoglobulin or placebo packets	5 grams (1-packet) per each dose*	PO	Twice a day for 12 weeks (3 cycles)	Every 4 weeks

*total dose is 10 grams per day

** Patients must begin taking agent/placebo within 7 days of registration (exceptions can be made if delays occur related to shipping agent/placebo and should be documented in the patient study record).

7.2 Patients can be instructed in administration techniques and granted intervention independence with nursing staff approval.

7.3 Patients will be instructed to add the contents of one packet (5 grams) to a cup and dissolve the powder with approximately one-half cup (4 fl. ounces, or 120 mL) of water. The patient will stir to mix and drink the contents. The patient will take one dose twice a day, in the morning and evening, with or without food.

7.4 Breaking Codes in Double-Blinded Studies-The intervention code may *not* be broken except for emergencies.

In the event of an emergency, call the MCCC Registration Office at [contact] to break the code on Monday through Friday, 8:00 a.m. to 4:30 p.m. Central Time. If the code must be broken after hours, assume the patient was assigned to active treatment and treat accordingly. Place a call to the MCCC Registration Office and leave a message informing them of the need to un-blind a patient. Provide your contact information so that MCCC Registration Office personnel can return the call the next business day.

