be converted to 100 and a score of 0 will remain as 0. This QOL will be measured weekly for the entire 12 week length of the study and at the end of the intervention. QOL improvement will be defined as at least a 10 point increase in the QOL score from baseline, on the percentage scale. This 10 point change represents a clinically meaningful improvement in QOL based on work done by Jeff Sloan [17]. The date at which the QOL score is first known to increase by at least 10 from baseline (on the 100 point scale), will be considered the event date for the purpose of analysis. Patients without at least a 10 point increase in QOL from baseline, will be censored on their last QOL evaluation date up to a maximum of 12 weeks. We will enter a total of 70 evaluable patients (35 per arm) using a 1:1 randomization scheme. The primary analysis will be a comparison of oral SBI vs. placebo using a two-sided log-rank test between the 2 Kaplan-Meier curves [18]. This analysis will take place after an approximate 16 month accrual period, and after 66 total events across both arms combined (which should happen after about 12 weeks of follow-up in all evaluable patients). Additionally, we assume a constant accrual rate over the course of the study, and that no patients will drop-out of the study, since historically the lost to follow-up rate is <1%. To determine the appropriate sample size of 35 evaluable patients per arm, we assumed exponential survival and that the median time-to-QOL improvement is around 3 weeks in the oral SBI arm and 6 weeks in the placebo arm (HR=2). This hazard ratio is based on our institution's data which shows that patients often begin postoperative chemotherapy 6 weeks after surgery. These assumptions yield 80% power to detect a significant difference between the arms using a 2-sided log-rank test at alpha=0.05. All patients who meet the eligibility criteria, sign the consent form, and are randomized, will be considered evaluable for this endpoint. All eligible patients will be followed a maximum of 12 weeks. If the 2-sided log-rank test p-value is < 0.05 showing significantly shortened time-to-QOL improvement in the oral SBI arm as compared to placebo, further study will be warranted. Of course, any final decisions will be based on all primary and secondary endpoints.

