16.64 **Translational Component:** The hypothesis is that oral SBI will improve postoperative recovery. However, we know of no biomarkers indicative of postoperative recovery. Hence in an exploratory manner, we will measure a host of candidate biomarkers. This study will include serial assessment at baseline, at a mid-way timepoint, and at the end of the intervention intervention. The differences between biomarker values over time will be compared between the 2 intervention arms using a Wilcoxon Rank-sum test. In addition, other graphical and statistical methods will be used to compare the data over time between oral SBI and placebo. All these analyses will be considered hypothesis-generating.

16.7 **Inclusion of Women and Minorities**

16.71 This study will be available to all eligible patients, regardless of race, or ethnic origin.

16.72 There is no information currently available regarding differential effects of this regimen in subsets defined by race, or ethnicity, and there is no reason to expect such differences to exist. Therefore, although the planned analysis will, as

always, look for differences in intervention effect based on racial groupings, the sample size is not increased in order to provide additional power for subset analyses.

16.73 The geographical region served by the Mayo Clinic has a population which includes approximately 5% minorities. We expect about 5% of patients will be classified as minorities by race and all will be women. Expected sizes of racial subsets are shown in the following table:

Accrual Estimates by Ethnicity/Race

Ethnic Category	Sex/Gender			
	Females	Males	Unknown	Total
Hispanic or Latino	0	0	0	0
Not Hispanic or Latino	100	0	0	100
Ethnic Category: Total of all subjects	100	0	0	100
Racial Category				
American Indian or Alaskan Native	0	0	0	0
Asian	2	0	0	2
Black or African American	3	0	0	3
Native Hawaiian or other Pacific Islander	0	0	0	0
White	95	0	0	95
Racial Category: Total of all subjects	100	0	0	100

Ethnic Categories: **Hispanic or Latino** – a person of Cuban, Mexican, Puerto Rican, South or Central American, or other Spanish culture or origin, regardless of race. The term “Spanish origin” can also be used in addition to “Hispanic or Latino.”

- **Not Hispanic or Latino**

Racial Categories: **American Indian or Alaskan Native** – a person having origins in any of the original peoples of North, Central, or South America, and who maintains tribal affiliations or community attachment.

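### Time from surgery to baseline can vary within the first postoperative week, but the primary, QOL and biomarker comparisons ignore it; the cost is precision, not validity

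*Combined protocol and SAP*

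**What the plan says.** **Entry.** Section 3.14 requires surgery no more than "7 days prior to registration and that entailed more than a simple hysterectomy". Section 3.13 adds: "Patients must have begun postoperative oral intake of food prior to registration". Section 7.1 then allows a further gap: "Patients must begin taking agent/placebo within 7 days of registration", with exceptions for shipping delays. First dose can therefore fall about 7 + 7 = 14 days after surgery. The test schedule (4.0) puts the baseline questionnaire in the column for procedures up to 21 days before randomization. Nothing there ties the baseline PQL to a particular postoperative day.

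**Allocation.** Section 5.0 lists five factors: age, "Splenectomy and/or rectosigmoid resection: yes vs. no", optimal debulking, cancer type, and "Open laparotomy vs. laparoscopic surgery". Section 6.21 confirms that "The factors defined in Section 5.0 will be used as stratification factors". Days since surgery is not among them.

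**Analysis.** For the primary endpoint (16.11), "QOL improvement will be defined as at least a 10 point increase in the QOL score from baseline". The arms are compared by a two-sided log-rank test, with no covariate and no stratification stated. QOL changes (16.63) are compared by Wilcoxon rank-sum test. For biomarkers (16.64), "The differences between biomarker values over time will be compared between the 2 intervention arms using a Wilcoxon Rank-sum test". Both of those sections leave room for further graphical and statistical methods but name no covariate.

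**The concern.** Many PQL items (pain, nausea, energy, bowel function, getting about the house) would be expected to recover after surgery whatever the assigned arm. The event is a change from each patient's own baseline. A patient whose baseline is taken on day 1 or 2 may therefore have more natural improvement ahead of her than one whose baseline is taken on day 7. Inflammatory markers may behave in the same way.

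If so, days since surgery predicts the primary event, and its date is needed anyway to check eligibility. Leaving it out has two consequences. Unexplained variation between patients pulls the unadjusted comparison toward no difference and lowers power. A chance difference in entry day between two arms of 35 can also move the estimate in either direction. This pilot decides whether a larger study is warranted, so both matter.

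**Working it through.** **1. The plan's own figure.** Inputs from 16.11: HR 2, two-sided alpha 0.05, 80% power, 1:1 allocation. Schoenfeld's formula gives events = 4(1.960 + 0.842)² / (ln 2)² = 65.3, rounded up to 66. Power with 66 events is Φ(√66 × 0.693/2 − 1.960) = 80.4%. Both stated figures reproduce.

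**2. Events under the plan's medians.** With exponential times, medians of 3 and 6 weeks, and 12 weeks of follow-up, 1 − 2⁻⁴ = 0.9375 and 1 − 2⁻² = 0.75 of patients improve. Expected events are 35 × (0.9375 + 0.75) = 59.1, for a power of 75.9%. So the starting point for the comparison below is about 76%, before any entry-day effect.

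**3. Power with and without adjustment.** Assumptions: 35 per arm; entry day uniform on 1–7; the plan's medians at day 4; censoring at 12 weeks; each further day since surgery multiplies the improvement hazard by a fixed factor. The documents do not give that factor, so a range is shown. The log-rank test is compared with a Cox model containing arm and day. Two separate simulations were made. The first used 2,500 trials per setting, so the simulation error of each power is about 1 point.

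| Hazard factor per day | Day-7 relative to day-1 hazard (factor⁶) | Log-rank power, runs 1 / 2 | Adjusted Cox power, runs 1 / 2 | Difference in points |
|---|---|---|---|---|
| 1.00 | 100% | 76 / 76 | 75 / 76 | −1 / 0 |
| 0.95 | 74% | 76 / 77 | 75 / 75 | −1 / −2 |
| 0.90 | 53% | 72 / 72 | 74 / 74 | +2 / +2 |
| 0.85 | 38% | 71 / 70 | 75 / 73 | +4 / +3 |
| 0.80 | 26% | 63 / 65 | 72 / 74 | +9 / +9 |
| 0.70 | 12% | 49 / 52 | 69 / 72 | +20 / +20 |

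Unadjusted type I error was 4.7% at a factor of 0.90 and 5.2% at 0.80. The simulation treats event times as continuous and gives the Cox model the correct form for the day effect, which is favourable to adjustment.

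**4. Chance imbalance.** Entry day uniform on 1–7 has SD √((49 − 1)/12) = 2.0 days. The standard error of the difference in mean entry day between arms is 2.0 × √(2/35) = 0.48 days. A gap of half a day or more occurs in 2 × (1 − Φ(0.5/0.48)), or about 30% of trials. At a factor of 0.80, half a day changes the hazard ratio by 1 − 0.80^0.5 = 11%; at 0.95, by 2.5%. The standard error of the log hazard ratio is about 2/√59 = 0.26. The 11% shift (0.11 on the log scale) is thus a little over 0.4 of a standard error.

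**5. A different assumed model.** A two-component recovery curve was also simulated (500 trials per shape, standard error about 2.2 points per power). Power for the log-rank test, for Cox with days, and for Cox with days and baseline PQL was 41/46/49%, 53/53/55% and 37/40/39% for three shapes. The gain from days alone is 0 to 5 points. These curves recover faster than the plan assumes. With no treatment effect, 66–94% of day-1 entrants and 32–39% of day-7 entrants improve by week 2. The plan's 6-week placebo median implies 1 − 0.5^(2/6) = 21%. They illustrate the mechanism but do not measure this trial.

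**The case against.** An unadjusted log-rank test is valid in a randomized trial, and adjusting for one more prognostic variable is a matter of efficiency. The trial is a pilot, and its biomarker work is declared hypothesis-generating. Surgical extent and approach, which plausibly relate to when a patient starts eating, are already balanced. The documents contain no PQL recovery curve. That recovery is fastest in the first week is a reasonable assumption, not a finding. The larger gains need a day-7 hazard only 12–26% of the day-1 hazard, and nothing in the documents supports so steep a gradient. A Cox estimate reported beside the log-rank test also adds no power to a decision taken on the log-rank p-value.

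All of this stands, and it limits the size of the point. It does not remove it, because the omission is plain in all three analyses and the remedy is cheap.

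A reader might infer three stronger things:

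- **That the comparison is biased or its type I error inflated.** It is not. Entry precedes allocation, chance imbalance is already part of alpha, and the simulated error is near 5%.
- **That entry runs freely from day 0.** The text sets no lower limit, but the oral-intake rule makes day-0 entry unlikely.
- **That the allocation is defective.** With five factors already balanced for 70 evaluable patients, a sixth is not needed; a covariate does the work.

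**Conclusion.** The point holds as a question of precision. Days since surgery is a plausible predictor of a baseline-relative event, and it is ignored in the primary, QOL and biomarker comparisons. Under the plan's medians and entry spread over days 1–7, the gain in power from adjusting ranges from nothing to about 20 points. Values of 0–5 points cover daily hazard declines up to about 15%. The documents give no basis for choosing within the range. The simulations under the plan's medians adjust for day only, so they do not show what baseline PQL would add. No comparable power figure was calculated for the QOL and biomarker tests; there the argument is by analogy.

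**What to change.** **Primary endpoint.** The plan has no Cox model, so one must be written in before unblinding: arm, days from surgery to the baseline PQL, and baseline PQL, both continuous. Report its treatment hazard ratio with confidence interval beside the log-rank test. If the power gain is wanted for the decision itself, say explicitly that the Cox test of treatment replaces the log-rank test in 16.11. The adjusted hazard ratio is conditional on the covariates and need not equal the unadjusted one even in balanced arms, so a difference between them should not by itself be read as imbalance.

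**QOL and biomarkers.** The Wilcoxon test cannot take a covariate. Replace or supplement it with a regression, rank-based if the distributions require it, of change on arm, baseline value, and days from surgery to the baseline measurement or blood draw.

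**Reporting.** Tabulate days since surgery by arm. Confirm that the surgery date and the baseline PQL date are both recorded, not only that the eligibility criterion was met.

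**Cost.** SAP text and some programming, with no added visit or patient. The statistical price is an assumption of proportional hazards and of covariate form, two extra terms with about 59–66 events (roughly 20 events per model term), and a possible power loss of up to about 2 points, close to simulation error, if entry day proves to have little or no prognostic value.

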3.2 Exclusion Criteria

- 3.21 Symptomatic and/or untreated brain metastases.
- 3.22 Ongoing parenteral nutrition (receiving intravenous nutrition support at the time of enrollment). Note: patients may be receiving maintenance IV fluids.
- 3.23 Current enrollment in any other trial that entails the concurrent administration of any other agent designed to enhance postoperative recovery.
- 3.24 Allergy to beef.

4.0 Test Schedule

Tests and procedures	Active Monitoring Phase				Observation/crossover (ends after 16 weeks of total study participation)
	≤21 days prior to randomization	Day 1 of Cycle 2 and 3 (+/- 3 days)	Weekly from registration for 12 weeks total	At the end of intervention (+/- 3 days)	
Patient assessment (includes weight**)	X				
Adverse event assessment	X	X**		X**	X**
Pregnancy test ¹ (Serum)	X				
Hematology group					
HgB					
WBC	X				
PLT					
ANC					
Chemistry group					
Creatinine	X				
Patient Questionnaire					
Booklets ² , (Appendix 2-5)	X		X	X	X
Blood specimens (see Section 14.0) ^{3,R}	X	X*			

1. For women of childbearing potential only. Must be done ≤7 days prior to registration.
2. Patient questionnaire booklets **must** be used; copies are not acceptable for this submission. Patients are required to fill out the questionnaires at baseline, and weekly for the duration of study participation, (16 weeks total, includes patients who never started therapy).
3. Blood specimens will be collected and submitted at baseline. Kits are required. Baseline blood specimen is to be collected after consent and prior to patient receiving study agent.

R Research funded (see Section 19.0)

*These blood draws are optional but strongly recommended.

** If patient cannot return, this assessment can be done by phone by the study coordinator (includes patient reported weight). However, study questionnaires must be mailed back.

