In addition to submitting initial IRB approval documents, ongoing IRB approval documentation must be on file (no less than annually) at the Registration Office ([contact]). If the necessary documentation is not submitted in advance of attempting patient registration, the registration will not be accepted and the patient may not be enrolled in the protocol until the situation is resolved.

When the study has been permanently closed to patient enrollment, submission of annual IRB approvals to the Registration Office is no longer necessary.

6.14 Prior to accepting the registration, the registration/randomization application will verify the following:

- IRB approval at the registering institution
- Patient eligibility
- Existence of a signed consent form
- Existence of a signed authorization for use and disclosure of protected health information

6.15 Intervention on this protocol must commence at Mayo Clinic Rochester, under the supervision of a medical oncologist.

6.16 Intervention cannot begin prior to registration and must begin \leq 7 days after registration.

6.17 Pre-intervention tests/procedures (see Section 4.0) must be completed within the guidelines specified on the test schedule.

6.18 All required baseline symptoms (see Section 10.6) must be documented and graded.

6.19a Study agent is available on site

6.19b Blood draw kit is available on site.

6.19c Patient questionnaire booklet is available on site; copies are not acceptable for this submission.

6.19d At the time of randomization, the following will be verified:

- Patient has/not given permission for his/her blood sample(s) to be stored and used in future research of ovarian cancer at Mayo Clinic.
- Patient has/not given permission for his/her blood sample(s) to be stored and used in future research at Mayo Clinic to learn about, prevent, or treat any other health problems
- Patient has/not given Mayo Clinic permission to give his/her blood sample(s) to outside institutions

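### Baseline and weekly PQL booklets are not tied to the first dose, so recovery before any product counts as a primary event in both arms and dilutes the SBI-placebo contrast

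*Combined protocol and SAP*

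**What the plan says.** - **Measurement clock.** The Test Schedule (4.0) sets the questionnaires "Weekly from registration for 12 weeks total". Section 16.63 describes the same weekly series as post-randomisation. The baseline booklet is marked in the column for up to 21 days before randomisation.
- **Start of product.** Section 6.16 requires the first dose after registration and no more than 7 days later. The footnote to 7.1 says: "Patients must begin taking agent/placebo within 7 days of registration (exceptions can be made if delays occur related to shipping agent/placebo". No maximum is given for the exception. Section 6.19a lists, among the registration requirements, "Study agent is available on site", and 6.15 requires the intervention to commence at Mayo Clinic Rochester.
- **Primary event.** Section 16.11 takes as event date "The date at which the QOL score is first known to increase by at least 10 from baseline", with a 12-week maximum. Nothing requires that dosing has begun. All eligible, consented, randomised patients are evaluable. No time zero is named beyond the reference to baseline.
- **Timing of surgery.** Section 3.14 places surgery at most 7 days before registration.
- **Adverse event window.** Section 16.61 covers patients who started therapy and counts 16 weeks from randomisation, explained as 12 weeks of intervention plus 1 month.

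**The concern.** The primary objective (2.11) concerns patients who are receiving SBI or placebo. Yet these clocks leave an untreated interval between baseline and first dose, and it falls in early convalescence. SBI cannot have caused an improvement in that interval, but the improvement is still a primary event. Such events occur at the same rate in both arms, so they pull the hazard ratio towards 1 and use up informative events. At stake is a missed effect in a 70-patient pilot whose log-rank result helps decide whether further study is warranted.

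The same lag shortens the adverse event window relative to exposure. If product starts on day 7, 12 weeks of product end at week 13 and the further 4 weeks end at week 17, one week outside the stated 16.

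**Working it through.** **Inputs from 16.11.** "We will enter a total of 70 evaluable patients (35 per arm) using a 1:1 randomization scheme"; medians of 3 weeks (SBI) and 6 weeks (placebo), exponential, HR 2; analysis "after 66 total events across both arms combined"; no dropout; 12-week cap.

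**The plan's own figure.** Schoenfeld events = 4 × (1.960 + 0.842)² / (ln 2)² = 65.3, so 66. Power with 66 events is 80.4%. The statement "These assumptions yield 80% power to detect a significant difference between the arms using a 2-sided log-rank test at alpha=0.05" therefore reproduces if 66 events are reached.

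**Effect of the 12-week cap alone.** Expected events = 35 × [(1 − 2^(−12/3)) + (1 − 2^(−12/6))] = 35 × (0.9375 + 0.75) = 59.1. Power = Φ(√59.1 × ln 2 / 2 − 1.96) = 76%. This is the no-lag reference; the loss from 80% to 76% is not due to the lag.

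**Assumptions for the lag, not in the documents.** Time runs from registration/randomisation. SBI patients have the placebo hazard until first dose and the 3-week-median hazard afterwards. The lag itself is varied.

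**Worked case: every patient waits 7 days.** The weekly hazards are ln 2/6 = 0.1155 and ln 2/3 = 0.2310.
- Share improving before dosing: 1 − exp(−0.1155) = 10.9%, or 70 × 0.109 = 7.6 events.
- SBI median from registration: 1 + (0.6931 − 0.1155)/0.2310 = 3.5 weeks.
- Expected events: 35 × [0.75 + 1 − exp(−0.1155 − 11 × 0.2310)] = 58.8, of which 7.6/58.8 = 13% are pre-dose.
- Average HR: exp(0.6931 × 51.2/58.8) = 1.83.
- Power: Φ(51.2 × 0.6931 / (2 × √58.8) − 1.96) = 64%.

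**Simulation.** Log-rank test, 35 per arm, events dated to the next weekly booklet, 12-week cap, 4,000 to 6,000 trials per scenario (standard error under 1 point):

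| Lag to first dose | Improved before dosing | Power |
|---|---|---|
| None | 0% | 76% |
| Uniform 0-7 days | about 5.5% | about 70% |
| 7 days, every patient | 11% | 62% |
| 14 days, every patient | 21% | about 50% |

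**The other reading of the medians.** Section 16.11 does not say that the medians run from first dose. Suppose the SBI median stays at 3 weeks from registration despite the lag. The post-dose HR must then be 6 × (1 − L/6)/(3 − L) for a lag of L weeks: 2.2 at 3.5 days and 2.5 at 7 days. Simulated power with the lag is about 80% and 86%. With the same post-dose HR and no lag it is about 85% and 95%.

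**Adverse event window.** Lag + 12 weeks + 4 weeks exceeds 16 weeks by exactly the lag.

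**The case against.** Timing every randomised patient from randomisation is conventional intention-to-treat practice and protects type I error. That stands. A reader might infer bias in favour of one arm, or a false-positive risk; assignment is randomised and blinded, so the documents support neither.

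The size is easily overstated. A reader might take 62% or 50% as the trial's power. The first needs every patient to start on day 7, and the second needs a 14-day shipping delay for everyone, which 7.1 treats as a documented exception. Sections 6.15 and 6.19a are consistent with short lags. Assuming faster natural recovery (a placebo median of 2 or 3 weeks) makes the loss larger, but those medians are not in the plan.

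A reader might also suppose that the week 1 booklet routinely precedes the first dose. It does so only with a start on day 7 or later. With shorter lags the booklet follows dosing but can still record improvement that took place before it.

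If the 3-week SBI median already runs from registration, the stated design loses nothing against its own target. This is fair, and the documents do not settle it. Even so, the last comparison in the working shows that removing the lag would raise power by about 5 to 9 points.

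Finally, it is tempting to move time zero to first dose after randomisation. That would mix two baselines and two clocks, because patients who never start still need a rule, and a later and higher baseline leaves less room for a 10-point rise. No gain in power has been shown for that approach.

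**Conclusion.** The misalignment is real and moderate. The schedule permits untreated recovery to count towards the primary event in both arms, and the sample size makes no allowance for it. On the plan's medians, with HR 2 acting only after first dose, the cost is about 6 points of power for a lag uniform over 0-7 days and about 14 points as the bound when every patient waits 7 days, both measured from 76%. The actual lag distribution is unknown.

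The baseline window adds to the problem. With baseline allowed up to 21 days before randomisation and surgery at most 7 days before registration, the wording does not exclude a pre-surgery baseline. A reader might infer that such baselines are intended; the documents do not say so, only that the window allows them.

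The validity of the test is not in question. The adverse event window does fall short of its own definition, by the length of any lag.

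**What to change.** 1. Complete the baseline PQL and randomise on the day of the first dose, before that dose, with product in hand, as 6.15 and 6.19a already suggest. Randomisation, baseline and first dose then share one time zero, and every randomised patient stays in the primary analysis. Name that time zero in 16.11 and narrow the baseline window for the booklet in 4.0 to match.
2. If a same-day start is not possible, keep randomisation as time zero for the primary analysis, report the lag by arm, and use a repeat PQL just before first dose as a sensitivity analysis only.
3. Count the 16.61 adverse event window from first dose. That analysis set is already limited to patients who started therapy, so nobody is lost. Bring the 16-week participation limit in 4.0 into line.
4. Reconcile 6.16 (7 days without exception), 6.19a (agent on site) and the shipping exception in 7.1.

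The cost is one amendment to 4.0, 6.1, 7.1, 16.11 and 16.61, and tighter scheduling within the 7-day surgery window of 3.14. The first option needs no extra booklet; the second needs one per patient.
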